#### 7.5 RANDOMISATION

Allocation of participants to trial groups will be done using the same web-based randomization system used in our pilot trial. Patients will be stratified by centre and diabetes. The randomization process will consist of a computer-generated random listing of the group allocations stratified as above in variable permuted block sizes that will not be known to the investigators. The system will have backup in the form of a statistician and designated research assistant at the coordinating centre and only these individuals will know the randomization codes. After confirming eligibility and obtaining consent, the study nurse will access the trial website and provide the subject's unique ID. The web site will provide the next available randomization number.

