### **10.2 POWER CALCULATIONS**

We conservatively estimate an average MACE rate of 6%: MACE rates in the U.S. range from 8.7 % in the first year after a kidney transplant to 13.2 % per year on the waiting list.(41) Unpublished data in Australia and Canada show lower rates of 3% and 8% respectively. The lowest MACE rate would be observed if *all* patients underwent transplantation rapidly (i.e. one year wait-listing (MACE 8%), followed by one year of post transplant follow up (MACE 3%)). In this hypothetical scenario, the

[figure not shown]
average MACE rate would be 5.5%. We estimate that 50% of participants will receive a kidney transplant during the study - therefore the majority of patient follow up time will be accrued on the waiting list (when the MACE rate is high) rather than after a KTX justifying our estimated average MACE rate of 6%.

Using a MACE rate of 6% per year and non-inferiority defined as a Hazard Ratio (HR) of MACE  $< 1.25$ , randomization of **3306 patients** will give us 80% power using a two-sided 5% significance level to claim no screening is non-inferior to regular screening if the absolute difference in MACE in the no screening group is  $< 1.4\%$  higher (i.e. 7.4% versus 6.0 %) than in the regular screening group (Fig 2). This is lower than the 2% absolute increase in MACE Canadian transplant physicians indicated would be unacceptable in a survey prior to our pilot trial.

Enrolment of 3306 patients requires recruitment of  $\leq 4$  patients per month per centre. This rate is feasible, and was achieved in our pilot trial. Figure 2 shows the study power for MACE rates between 5 -13% per year. These calculations take into account the different study follow-up in Canada (5 years) and Australasia (4 years), and allow for a 10% drop-out rate.

Power calculations were performed using the **Non-inferiority Logrank Tests** in PASS 12 (NCSS, LLC. Kaysville, Utah, USA. [www.ncss.com](http://www.ncss.com)).

Figure 2: Study power for MACE rates

- For all power calculations, non-inferiority is defined as an absolute increase in the Hazard Ratio (HR) of MACE  $< 1.25$ , Two-sided alpha is 5%, and the total sample size is fixed at N=3306

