### 10.3 STATISTICAL METHODS TO BE UNDERTAKEN

Efficacy outcomes will be analysed using intention to treat. A significance level of 5% shall be used for all analyses, unless otherwise specified. All analyses will be adjusted for site.

The primary analysis will be an analysis of the time to first occurrence of the primary outcome MACE, using a Cox model with treatment arm as a covariate and stratified by site. This analysis will provide an estimate of the HR, a p-value and CI. Non-inferiority will be claimed if the 95%CI of the HR lies entirely lower than an HR value of 1.25, with the screening arm being the referent group. Superiority will be claimed if the 95%CI lies entirely lower than 1. Proportional hazards assumption will be assessed using log-log survival plots and Schoenfeld residuals.

The outcome of all-cause mortality will also be analyse using a Cox model. The time to all other outcomes will be analysed using a competing risk model, with the competing risk being death. Outcomes which can occur more than once will also be analysed using an Andersen and Gill model (42). This model is a natural extension of the Cox model and unlike the Poisson or Negative Binomial models for count data, does not require the assumption of a constant event rate over time. Robust standard errors using the Sandwich estimator will be applied to ensure the correct p-value and CIs are calculated.

All time to event data will also be graphically summarised using a Kaplan Meier or cumulative incidence curves comparing the two treatment arms.

For all time to event outcomes, a subgroup analysis will conducted to test for a statistical interaction (effect modification) between treatment arm and transplantation. This will be performed by stratifying the survival models by transplant date and testing the HRs between the two strata.

Time off waiting list will be analysed using a negative binomial model, with an offset for total time in study.

Safety outcomes will also be analysed using both intention to treat and per-protocol approaches.

Balance between treatment arms will be assessed by comparing means for continuous variable characteristics, such as age, or by comparing proportion for categorical characteristics, such as sex. If there is any imbalance, then an adjusted analysis for any unbalanced characteristics will be conducted in addition to the analyses stated above, which only account for site.

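### Adjustment beyond site is chosen by observed baseline imbalance, and diabetes, a randomisation stratum, is in no planned model

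*Protocol*

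**What the plan says.** Protocol section 10.3 defines the primary analysis as time to first MACE, "using a Cox model with treatment arm as a covariate and stratified by site". It attaches the decision rule to that model: "Non-inferiority will be claimed if the 95%CI of the HR lies entirely lower than an HR value of 1.25". The same section adjusts every analysis for site and names no other covariate.

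Its last paragraph deals with baseline balance: "Balance between treatment arms will be assessed by comparing means for continuous variable characteristics, such as age", with proportions compared for categorical characteristics such as sex. It continues: "If there is any imbalance, then an adjusted analysis for any unbalanced characteristics will be conducted in addition to the analyses stated above". The analyses already described are those "which only account for site".

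Section 7.5 names two randomisation factors, not one: "Patients will be stratified by centre and diabetes". Only centre reappears in section 10.3.

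**The concern.** Three features of the rule are weak.

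- **Selection by chance.** In a properly randomised trial a baseline difference between arms is a chance event. A covariate earns its place by predicting the outcome. This rule can admit a factor that differs by chance and is irrelevant to MACE, and leave out a strong predictor that happens to be balanced.
- **Selection after the fact.** There is no threshold for imbalance and no closed list of characteristics, since age and sex are given only as examples. Nobody can write down the second model before the arms have been compared.
- **Diabetes is missed.** The trial treats diabetes as important enough to stratify on, then uses it in no planned model. Permuted blocks within centre-by-diabetes strata keep it balanced, so the trigger would normally not pick it up.

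At stake is the credibility of the supplementary hazard ratio (HR), which will be read beside the primary one against the 1.25 margin. There is also an avoidable mismatch between how patients are randomised and how they are analysed.

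**Working it through.** **1. The plan's own power figure.** Section 10.2 starts from an event rate ("Using a MACE rate of 6% per year") and a margin of HR 1.25, and states that 3306 patients "will give us 80% power using a two-sided 5% significance level".

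- Events needed if the true HR is 1 with equal allocation (the ratio is not stated): 4 × (1.960 + 0.842)² / (ln 1.25)² = 4 × 2.8016² / 0.2231² = 630.5, so 631.
- Events expected: exponential survival, 1100 patients followed up to 4 years and 2206 up to 5 years. Accrual length is not stated. With an assumed 2-year accrual and 10% loss over the whole of follow-up, 625 events are expected if 6% is read as a hazard and 642 if it is read as an annual risk. Power is 79.6% to 80.7%.

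The stated 80% therefore reproduces under a plausible reading, and nothing below disturbs it.

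**2. How often the trigger fires by chance.** The protocol sets no criterion. Assume that imbalance means p<0.05 on k independent characteristics. The chance of at least one is 1 − 0.95^k:

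| k | chance of firing |
|---|---|
| 5 | 23% |
| 10 | 40% |
| 15 | 54% |
| 20 | 64% |

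If the wording is taken literally and any difference counts, the second model would be run almost always.

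**3. What leaving out diabetes does.** Simulated trials had N = 3306, 23 sites, randomisation stratified by site and diabetes, up to 1 year of accrual and 10% loss over 5 years. Diabetes prevalence was 28%, the figure for transplant candidates in section 5.2. The diabetes HRs are assumptions. There were 1500 trials at true HR 1.25 and 1000 at true HR 1, so the Monte Carlo standard error is about 0.4 points for the false non-inferiority rate and 1.2 points for power.

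| Assumed diabetes HR | Model | Mean HR (true 1.25) | False non-inferiority | Power (true HR 1) |
|---|---|---|---|---|
| 1.5 | site | 1.249 | 2.1% | 82.4% |
| 1.5 | site and diabetes | 1.250 | 2.1% | 82.3% |
| 2.0 | site | 1.246 | 2.7% | 81.3% |
| 2.0 | site and diabetes | 1.250 | 2.9% | 80.9% |
| 2.5 | site | 1.245 | 2.3% | 80.9% |
| 2.5 | site and diabetes | 1.253 | 2.2% | 80.4% |

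Adding diabetes moves the HR by less than 0.01 and power by at most half a point. It does not narrow the interval: at diabetes HR 2.0 and true HR 1, the model standard error of the log HR is 0.0764 with site only and 0.0765 with both.

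**4. How often the triggered model changes the answer.** Ten further independent covariates were added, each with an assumed HR of 1.2 per SD, with diabetes HR 2.0 and the trigger at p<0.05.

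| Quantity | True HR 1.25 | True HR 1 |
|---|---|---|
| Trigger fired | 41% | 42% |
| Non-inferiority claimed, site-only primary model | 3.8% | 82.8% |
| Non-inferiority claimed, triggered model (primary result where not fired) | 3.7% | 83.0% |
| The two conclusions differ | 0.9% | 1.8% |
| Non-inferiority claimed, all covariates pre-specified | 2.3% | 81.5% |

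The trigger fires often, rarely changes the conclusion, and does almost none of what a pre-specified model would do.

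**The case against.** The best defence is that section 10.3 already protects the decision. It names the site-stratified Cox model as primary, ties the 1.25 rule to it, and runs the imbalance model only as an addition. That stands, and it rules out several stronger readings that a reader might infer.

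- **That two HRs compete with no order of precedence.** They do not. The primary model is identified and fixed in advance, so the trigger leaves its type I error untouched.
- **That 40% to 64% is the chance of a changed conclusion.** It is only the chance that a supplementary model is run, under assumed 5% tests. The section speaks of comparing means and proportions and does not expressly call for tests. Its general 5% level might be taken to cover them, but that is an inference.
- **That omitting diabetes costs precision or validity.** The simulations show no gain in power or interval width from adding it.
- **That diabetes could never enter.** Incomplete blocks across the 46 site-by-diabetes strata (23 × 2) can leave small differences, so the accurate word is normally.
- **That site-only adjustment inflates false non-inferiority from 2.3% to 3.8%.** That contrast needs ten assumed covariates, and it applies the margin to the fully conditional HR, which the protocol does not say. It also does not measure the benefit of adding only diabetes, age and sex.

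It could also be said that covariate detail belongs in the statistical analysis plan. That does not answer the point, because the protocol itself states the imbalance rule and the site-only adjustment. A later plan must either inherit them or depart from them.

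**Conclusion.** The point holds as a defect in the supplementary analysis and as a mismatch between randomisation and analysis. It is not a threat to the primary test. The protocol lets chance imbalance choose the covariates after the data are seen, and it leaves a randomisation stratum out of every planned model.

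The size is modest. The trigger would fire in 40% to 64% of trials under assumed 5% tests of 10 to 20 independent characteristics. Disagreement on non-inferiority occurred in 0.9% to 1.8% of simulated trials with ten characteristics, and omitting diabetes alone made a negligible numerical difference. The figures rest on assumed covariate and diabetes effects, accrual length and equal allocation, none of which the protocol gives. The case for the change is that it removes a post hoc choice at essentially no cost.

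**What to change.** In section 10.3:

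1. Delete the sentence that makes adjustment depend on imbalance, and keep the baseline comparison as description only.
2. Carry both randomisation factors, site and diabetes, into the primary Cox model, as strata or as covariates. With 46 strata there are on average about 72 patients each (3306 / 46). If small sites would make strata thin, entering diabetes as a covariate within site strata avoids this.
3. Pre-specify one supportive Cox model that adds age and sex whatever the observed balance.
4. State that the non-inferiority decision rests on the primary model alone, so that the supportive HR cannot be read as a second test.

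The cost is a few lines of text. Diabetes is known at randomisation, and age and sex are already named as baseline characteristics, so no new data are needed and the sample size is unchanged. The primary HR becomes conditional on diabetes, which moved it by less than 0.01 in the simulations.

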## **11. DATA SECURITY & HANDLING**

### **11.1 DETAILS OF WHERE RECORDS WILL BE KEPT & HOW LONG WILL THEY BE STORED**

Data will be captured using REDCap and stored on servers at the Sydney Local Heath District (SLHD) Royal Prince Alfred data centre. Participating sites will enter data into electronic case report forms (eCRF) via a secure web-based data capture software tool. REDCap allows data to be inputted at multiple sites with web authentication, data logging and Secure Sockets Layer encryption. Records will be kept for a minimum of 15 years.

The coordinating site will generate periodic data audit for quality and accuracy and provide data reports required for progress reports, data safety monitoring board meetings and event adjudication committee meetings.

## 11.2 CONFIDENTIALITY AND SECURITY

The coordinating site will monitor data inputted by contributing sites. Users are given individual usernames and passwords and are granted access to the project with certain privileges. Data collected from individual sites will be anonymous and de-identified. Confidential data such as patient details will also be de-identified during the export mechanism to allow data to be analysed. The backup process is maintained by SLHD Information Management and Technology Division and are performed daily to a separate server.

## 11.3 ANCILLARY DATA

Ancillary data such as test reports will be uploaded onto the eCRF and will stored electronically via the mechanism outlined above.

## 1. APPENDIX

### List of Attachments included:

Document Name	Version Number	Date (e.g., 18 January 2012)
QOL-Health Questionnaire - EQ-5D-5L	1.0	June, 2015
Kidney Disease and Quality of Life – KDQOL-36	1.0	2000

